8.2.7 Power

Primary Safety: If a serious (Grade 3 or Grade 4) adverse experience occurs at a rate of 1%, 5% or 10% then the chance of observing such an adverse event among the various possible sample sizes are provided in [Table 13](#).

Table 13 Probability of Observing Serious Grade 3 or Grade 4 Adverse Experience for Various AE Rates

| Serious AE Rate | Probability (%) of observing serious AE among MK-3475 treated patients | | | | |
|-----------------|--|---------------|---------------|---------------|---------------|
| | $n_{MK} = 12$ | $n_{MK} = 15$ | $n_{MK} = 18$ | $n_{MK} = 24$ | $n_{MK} = 33$ |
| 1% | 11 | 14 | 17 | 21 | 28 |
| 5% | 46 | 54 | 60 | 71 | 82 |
| 10% | 72 | 79 | 85 | 92 | 97 |

n_{MK} = final number of patients receiving neoadjuvant MK-3475

If no AE of a given type is observed in any subject receiving neoadjuvant MK-3475, then the true incidence of the adverse experience at that dose is at most 13%, 10%, 9%, 6%, or 5% with 80% confidence when the sample size among those receiving neoadjuvant MK-3475 is 12, 15, 18, 24 or 33, respectively.

Primary PD:

Table 14 shows the cumulative probabilities of stopping and declaring success on the primary PD hypothesis after each interim analysis assuming various true immune cell infiltration response rates and implementing the interim analysis strategy as described in Section 8.2.6. If the true immune infiltration response rate is 40%, there is ~85% power to meet the primary hypothesis at either the second or third interim analysis, or at the end of the study. If the true response rate is 45%, there is ~85% to meet the primary hypothesis at either the second or third interim analysis. To have high power (>80%) to meet the primary hypothesis after the second interim analysis, the true response rate must be greater than or equal to 55%.

Table 14 Cumulative Probabilities of Stopping and Declaring Success After Each Interim Analysis Assuming Various True Immune Cell Infiltration Response Rates

| True immune cell infiltration response rate | Probability (%) of stopping and declaring success (obtaining stated level of posterior probability that the true immune cell infiltration response rate of MK-3475 at least 30%) | | |
|---|--|------------|-----------------|
| | After IA 2 | After IA 3 | At end of study |
| 5% | <0.1 | <0.1 | <0.1 |
| 10% | <0.1 | <0.1 | 0.1 |
| 15% | 0.3 | 0.7 | 1.0 |
| 20% | 1.7 | 4.3 | 6.6 |
| 25% | 6.3 | 14.4 | 22.0 |
| 30% | 13.0 | 29.4 | 44.0 |
| 35% | 25.5 | 50.1 | 67.5 |
| 40% | 39.2 | 69.3 | 84.8 |
| 45% | 53.6 | 83.7 | 94.6 |
| 50% | 68.7 | 92.8 | 98.5 |
| 55% | 82.0 | 97.5 | 99.8 |
| 60% | 90.1 | 99.2 | >99.9 |
| 65% | 95.3 | 99.8 | >99.9 |
| 70% | 98.3 | >99.9 | >99.9 |

IA = interim analysis

If the second interim analysis sample size is 12 (15) receiving neoadjuvant MK-3475, at least 80% posterior probability that the true immune cell infiltration response rate is 30% will be obtained if at least 6 (7) patients respond. If the third interim analysis sample size is 18 (24) receiving neoadjuvant MK-3475, at least 70% posterior probability that the true immune cell infiltration response rate is 30% will be obtained if at least 7 (9) patients respond. If the final analysis sample size is 24 (33) receiving neoadjuvant MK-3475, at least 60% posterior probability that the true immune cell infiltration response rate is 30% will be obtained if at least 6 (11) patients respond. Therefore, the analyses supporting the secondary and tertiary hypotheses will have as few as 6 responders.

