8.2.4 Statistical Methods

Primary Safety

Incidence of adverse experiences will be descriptively summarized for all adverse experiences and Grade 3 or 4 adverse experiences separately. Summary statistics and plots will be generated for the change from baseline values in the vital signs, ECG parameters, and selected laboratory safety parameters for subjects, as deemed clinically appropriate. Depending on the safety parameter, the difference from baseline will either be computed on the original scale (raw change from baseline) or on the log scale and back-transformed for reporting (percent change from baseline). Summary statistics for the raw laboratory safety tests, ECGs, and/or vital signs may also be computed, as deemed clinically appropriate.

The incidence of intra- and postoperative complications will also be determined. Intra- and postoperative complications are not uncommon in patients undergoing surgical RCC resection, even in those proceeding directly to surgery without any neoadjuvant therapy. In a report of 58 such patients, the transfusion rate was 62.1% (median of 3.5 ± 6.6 units of blood products), and the complication rate was 27.6%, consisting of the need for surgical reexploration (5.2%), hospital readmission (8.6%), thromboembolic complications (1.7%), cardiovascular complications (3.4%), pulmonary complications (6.9%), gastrointestinal complications (10.3%), infectious complications (3.4%) and incision-related complications (6.9%) [79]. The incidence of surgical complications for patients receiving neoadjuvant MK-3475 will be summarized and contrasted with these published complication rates, as the total number subjects in this trial as well as the limited number of untreated controls will be of insufficient power to make accurate within study comparisons.

Primary PD

To assess the primary PD hypothesis, the posterior probability that the true response rate is at least 30% will be calculated based on a beta-binomial Bayesian model. A beta prior with parameters $\alpha=0.1$ and $\beta=0.1$ will be assumed. The primary PD hypothesis will be met with at least 80% posterior probability at interim analysis 1, at least 70% posterior probability at interim analysis 2, or at least 60% posterior probability at interim analysis 3. Additional sensitivity analyses may be performed where the definition of a responder is varied from 2-fold or greater increase in intratumoral lymphocytic infiltration to increases less than 2-fold.

Secondary PD

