8.2.5 Multiplicity

Since there is only one primary PD hypothesis, no multiplicity adjustment will be made when testing the primary hypothesis. The secondary and tertiary PD hypotheses will only be tested if the primary PD hypothesis is met. There are six separate secondary hypotheses and more than 8 tertiary hypotheses. Benjamini and Hochberg's false discovery rate multiplicity

adjustment will be applied at a rate of 10% when testing the secondary and tertiary hypotheses.

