The second interim analysis will occur after a total of 18 RCC patients have undergone tumor resection, with either 15 receiving neoadjuvant MK-3475 with 3 controls or 12 receiving neoadjuvant MK-3475 with 6 controls. The primary PD hypothesis will be assessed, and success will be declared and enrollment may stop if there is at least 80% posterior probability that the true response rate is at least 30%. If success cannot be declared after the initial 18

patients, an additional 9 patients may be enrolled and randomized as determined by the results of the first interim analysis, and a third interim analysis will occur after 27 RCC patients have undergone tumor resection, with either 24 receiving neoadjuvant MK-3475 with 3 controls or 18 receiving neoadjuvant MK-3475 with 9 controls. The primary hypothesis will be assessed, and success will be declared and enrollment may stop if there is at least 70% posterior probability that the true response rate is at least 30%. If success cannot be declared after the initial 27 patients, an additional 9 patients may be enrolled and randomized as determined by the results of the first interim analysis. The final analysis will be performed after 36 RCC patients have undergone tumor resection. At the final analysis, success will be declared if there is at least 60% posterior probability that the true response rate is at least 30%.

After each interim analysis, decisions related to enrolling additional patients may deviate from the rules defined above based on the accumulating data, at the discretion of the Sponsor.

In addition, decisions related to stopping the study for futility may also be considered at each interim analysis. At the second interim analysis, if there are only 0 or 1 responders the study may be stopped for futility. The probability of this happening when the true response rate is 30% is 8.5% (3.5%) with a sample size of 12 (15). At the third interim analysis, if there are 2 or less responders the study may be stopped for futility. The probability of this happening when the true response rate is 30% is 6.0% (1.2%) with a sample size of 18 (24).

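### Section 8.2.7 gives 6 of 24 responders as enough for the final 60% posterior criterion; under the stated prior 6 of 24 gives 27.6% and the minimum is 8

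*Combined protocol and SAP*

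**What the plan says.** Section 8.2.4 sets the model: "the posterior probability that the true response rate is at least 30% will be calculated based on a beta-binomial Bayesian model". It also sets the prior: "A beta prior with parameters $\alpha=0.1$ and $\beta=0.1$ will be assumed". Section 8.2.6 sets the last decision rule: "success will be declared if there is at least 60% posterior probability that the true response rate is at least 30" percent.

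Section 8.2.7 then lists the responder counts said to satisfy the rule at each stage. There are two counts per stage because the number of treated patients depends on whether the control arm is kept after the first interim analysis:

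- Second interim, 80%: 6 of 12, or 7 of 15.
- Third interim, 70%, with 18 (24) treated: this "will be obtained if at least 7 (9) patients respond".
- Final, 60%, with 24 (33) treated: the text says the required "posterior probability that the true immune cell infiltration response rate is 30% will be obtained if at least 6 (11) patients respond".

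Section 8.2.5 makes the primary result a gate: "The secondary and tertiary PD hypotheses will only be tested if the primary PD hypothesis is met".

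**The concern.** The printed 6 of 24 looks wrong before any calculation. It is an observed rate of 25%. With a prior worth only 0.2 of an observation, that cannot give a 60% probability that the true rate is 30% or more.

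It also clashes with the count before it. On the branch that keeps controls, the third interim analysis requires 7 of 18. Under the Section 8.2.6 thresholds a trial with 6 of 18 does not succeed there and may enrol six more treated patients. If none of the six responded, the trial would finish at 6 of 24 and, by the printed count, would now succeed.

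Section 8.2.7 is the only place where the posterior rule is expressed as counts, so it is a natural look-up table. At 6 or 7 responders of 24 a reader of Section 8.2.6 would declare the primary PD hypothesis not met, and a reader of Section 8.2.7 would declare it met and open the secondary and tertiary testing.

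**Working it through.** **Inputs.** Prior Beta(0.1, 0.1) (Sections 8.1 and 8.2.4); target rate 30%; thresholds 80%, 70% and 60% at the second interim, third interim and final analyses (Section 8.2.6); treated numbers 12/18/24 or 15/24/33 (Sections 8.2.6 and 8.2.7).

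**Formula.** With r responders among n treated patients the posterior is Beta(0.1 + r, 0.1 + n − r), so

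P(rate ≥ 0.30 | r, n) = 1 − F(0.30; 0.1 + r, 0.1 + n − r), where F is the beta distribution function.

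**Step 1: the six printed counts.**

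| Stage and threshold | n | Printed count | Posterior at printed count | Posterior one lower | True minimum |
|---|---|---|---|---|---|
| Second interim, 80% | 12 | 6 | 92.4% | 79.5% | 6 |
| Second interim, 80% | 15 | 7 | 90.9% | 78.5% | 7 |
| Third interim, 70% | 18 | 7 | 78.0% | 60.4% | 7 |
| Third interim, 70% | 24 | 9 | 77.5% | 62.4% | 9 |
| Final, 60% | 33 | 11 | 64.9% | 50.1% | 11 |
| Final, 60% | 24 | 6 | **27.6%** | 14.1% | **8** |

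Five of the six are exact minima, so the formula is the plan's own method. For n = 24 the sequence is 27.6% at 6, 44.7% at 7, 62.4% at 8 and 77.5% at 9.

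**Step 2: could another prior explain it?** With Beta(0.5, 0.5), Beta(1, 1), Beta(0.01, 0.01), a prior close to Beta(0, 0), Beta(0.3, 0.7), Beta(0.1, 0.2) and Beta(3, 7), the posterior at 6 of 24 never exceeds 34.1%. The minimum is 8 throughout, except 9 under Beta(3, 7).

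**Step 3: how often it matters.** Follow Section 8.2.6 without futility or discretionary stops, with one response rate for two and three doses. The n = 24 final analysis needs at least 4 of 6 at the first interim, then at most 5 of 12, then at most 6 of 18. At a true rate of 30%:

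- First six patients: P(4) = 0.05954 and P(5) = 0.01021. With 6 of 6 the trial has already succeeded by the second interim.
- For each further six patients: P(0) = 0.1176, P(1) = 0.3025, P(2) = 0.3241, P(3) = 0.1852.
- At 12 treated: total 4 has probability 0.05954 × 0.1176 = 0.00700; total 5 has 0.05954 × 0.3025 + 0.01021 × 0.1176 = 0.01921.
- Reaching the final: 0.00700 × (0.1176 + 0.3025 + 0.3241) + 0.01921 × (0.1176 + 0.3025) = 0.0133, or 1.3%.
- At 18 treated: totals 4, 5 and 6 have probabilities 0.00082, 0.00438 and 0.00808.
- Ending with exactly 6 or 7: 0.00082 × 0.5094 + 0.00438 × 0.6267 + 0.00808 × 0.4202 = 0.0066, or 0.66%.

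The same enumeration at other rates, with overall success under each cut-off for n = 24:

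| True rate | Reaches n = 24 final | Ends there with 6 or 7 | Success, cut-off 6 | Success, cut-off 8 | Table 14 |
|---|---|---|---|---|---|
| 20% | 0.8% | 0.48% | 7.5% | 7.0% | 6.6% |
| 30% | 1.3% | 0.66% | 44.7% | 44.1% | 44.0% |
| 40% | 1.0% | 0.31% | 85.1% | 84.8% | 84.8% |

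Over a fine grid of true rates, the largest difference in overall success is 0.68 percentage points, at 27.5%.

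**Step 4: Table 14.** It cannot show which cut-off was used. At 25% it prints 22.0%, between 22.3% (cut-off 6) and 21.6% (cut-off 8). Its second-interim column, where this cut-off plays no part, already differs from the exact values by as much as the two cut-offs differ (53.6% printed against 54.6% at a 45% rate).

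**The case against.** The best defence is that Section 8.2.7 only illustrates. Success is defined by posterior probability in Sections 8.2.4 and 8.2.6, and nothing says it will be declared by counting responders. PD analyses use the per-protocol set (Section 8.2.3), so the analysed number may not be exactly 24 and the posterior would have to be computed anyway. The branch is rare and power is unaffected. All of this stands, and it limits the weight of the point. It does not make the printed count correct.

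A second line is that the plan is not consistent about which stage carries which threshold. Sections 8.1 and 8.2.4 attach 80/70/60% to interim analyses 1, 2 and 3, while Section 8.2.6 attaches them to interim 2, interim 3 and the final analysis. Under the former labels 6 of 18 (60.4%) would pass the third interim, so the 6-of-18 example holds only under Section 8.2.6. The labels do not rescue 6 of 24, which misses all three thresholds.

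Against the rarity argument, the low frequency assumes strict adherence. Section 8.2.6 says only that later patients may all receive MK-3475, and it leaves enrolment decisions to the sponsor's discretion. If controls continued after fewer than 4 early responders, n = 24 at the final analysis would be more common. Once that analysis is reached, 6 or 7 responders is a likely result: 0.475/0.785 = 60% of such trials at a 20% rate, 0.656/1.329 = 49% at 30%, and 0.308/0.993 = 31% at 40%.

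**Conclusion.** The concern holds. The printed 6 of 24 is wrong by two responders: it carries a posterior probability of 27.6% against the 60% claimed, and the minimum is 8 (62.4%). This rests only on the stated prior, the 30% target and the 60% final rule of Section 8.2.6, and other plausible priors do not change it.

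The consequence is narrow. It is confined to 6 or 7 responders among 24 treated patients at the final analysis, where two sections of the plan disagree on the primary PD hypothesis and so on the gate to later testing. The size estimates assume strict adherence to Section 8.2.6, exactly 24 evaluable treated patients and one response rate for both dose schedules. The optional futility stops do not alter how often this analysis is reached, because every trial on this branch already has at least 4 responders. Because the figure is a pre-specified success count for a primary hypothesis, it should be corrected despite the small overall effect.

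**What to change.** In the last paragraph of Section 8.2.7, change the final-analysis count for 24 treated patients from 6 to 8, so that the pair reads 8 (11). The cost is one number. No design feature, sample size or entry in Table 14 changes on this account. The closing remark that later analyses may rest on only six responders also stays true, because 6 of 12 is enough at the second interim analysis.

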9.0 LABELING, PACKAGING, STORAGE AND RETURN OF CLINICAL SUPPLIES

9.1 Investigational Product

The investigator shall take responsibility for and shall take all steps to maintain appropriate records and ensure appropriate supply, storage, handling, distribution and usage of investigational product in accordance with the protocol and any applicable laws and regulations.

Clinical Supplies will be provided by the Sponsor as summarized in [Table 15](#).

Clinical supplies will be packaged to support enrollment and replacement subjects as required. When a replacement subject is required, the Sponsor or designee needs to be contacted prior to dosing the replacement supplies.

Table 15 Product Description

| Product Name & Potency | Dosage Form |
|------------------------|-----------------------|
| MK-3475 | Lyophilized 50mg/vial |

9.2 Packaging and Labeling Information

Clinical supplies will be affixed with a clinical label in accordance with regulatory requirements.

9.3 Clinical Supplies Disclosure

This trial is open-label; therefore, the subject, the trial site personnel, the Sponsor and/or designee are not blinded. Treatment (name, strength or potency) is included in the label text; random code/disclosure envelopes or lists are not provided.

9.4 Storage and Handling Requirements

Clinical supplies must be stored in a secure, limited-access location under the storage conditions specified on the label.

Receipt and dispensing of trial medication must be recorded by an authorized person at the trial site.

Clinical supplies may not be used for any purpose other than that stated in the protocol.

9.5 Returns and Reconciliation

The investigator is responsible for keeping accurate records of the clinical supplies received from the Sponsor or designee, the amount dispensed to and returned by the subjects and the amount remaining at the conclusion of the trial.

For all trial sites, the local country Sponsor personnel or designee will provide appropriate documentation that must be completed for drug accountability and return.

10.0 ADMINISTRATIVE AND REGULATORY DETAILS

10.1 Confidentiality

10.1.1 Confidentiality of Data

By signing this protocol, the investigator affirms to the Sponsor that information furnished to the investigator by the Sponsor will be maintained in confidence, and such information will be divulged to the institutional review board, ethics review committee (IRB/ERC) or similar or expert committee; affiliated institution and employees, only under an appropriate understanding of confidentiality with such board or committee, affiliated institution and employees. Data generated by this trial will be considered confidential by the investigator, except to the extent that it is included in a publication as provided in the Publications section of this protocol.

10.1.2 Confidentiality of Subject Records

By signing this protocol, the investigator agrees that the Sponsor (or Sponsor representative), IRB/ERC, or regulatory authority representatives may consult and/or copy trial documents in order to verify worksheet/case report form data. By signing the consent form, the subject agrees to this process. If trial documents will be photocopied during the process of verifying worksheet/case report form information, the subject will be identified by unique code only; full names/initials will be masked prior to transmission to the Sponsor.

By signing this protocol, the investigator agrees to treat all subject data used and disclosed in connection with this trial in accordance with all applicable privacy laws, rules and regulations.

10.1.3 Confidentiality of Investigator Information

By signing this protocol, the investigator recognizes that certain personal identifying information with respect to the investigator, and all subinvestigators and trial site personnel, may be used and disclosed for trial management purposes, as part of a regulatory submissions, and as required by law. This information may include:

1. name, address, telephone number and e-mail address;
2. hospital or clinic address and telephone number;

3. curriculum vitae or other summary of qualifications and credentials; and
4. other professional documentation.

Consistent with the purposes described above, this information may be transmitted to the Sponsor, and subsidiaries, affiliates and agents of the Sponsor, in your country and other countries, including countries that do not have laws protecting such information. Additionally, the investigator's name and business contact information may be included when reporting certain serious adverse events to regulatory authorities or to other investigators. By signing this protocol, the investigator expressly consents to these uses and disclosures.

If this is a multicenter trial, in order to facilitate contact between investigators, the Sponsor may share an investigator's name and contact information with other participating investigators upon request.

10.1.4 Confidentiality of IRB/IEC Information

The Sponsor is required to record the name and address of each IRB/IEC member that reviews and approves this trial. The Sponsor is also required to document that each IRB/IEC meets regulatory and ICH GCP requirements by requesting and maintaining records of the names and qualifications of the IRB/IEC members and to make these records available for regulatory agency review upon request by those agencies.

10.2 Compliance with Financial Disclosure Requirements

Financial Disclosure requirements are outlined in the US Food and Drug Administration Regulations, Financial Disclosure by Clinical Investigators (21 CFR Part 54). It is the Sponsor's responsibility to determine, based on these regulations, whether a request for Financial Disclosure information is required. It is the investigator's/subinvestigator's responsibility to comply with any such request.

The investigator/subinvestigator(s) agree, if requested by the Sponsor in accordance with 21 CFR Part 54, to provide his/her financial interests in and/or arrangements with the Sponsor to allow for the submission of complete and accurate certification and disclosure statements. The investigator/subinvestigator(s) further agree to provide this information on a Certification/Disclosure Form, commonly known as a financial disclosure form, provided by the Sponsor or through a secure password-protected electronic portal provided by the Sponsor. The investigator/subinvestigator(s) also consent to the transmission of this information to the Sponsor in the United States for these purposes. This may involve the transmission of information to countries that do not have laws protecting personal data.

10.3 Compliance with Law, Audit and Debarment

By signing this protocol, the investigator agrees to conduct the trial in an efficient and diligent manner and in conformance with this protocol; generally accepted standards of Good Clinical Practice (e.g., International Conference on Harmonization of Technical

Requirements for Registration of Pharmaceuticals for Human Use Good Clinical Practice: Consolidated Guideline and other generally accepted standards of good clinical practice); and all applicable federal, state and local laws, rules and regulations relating to the conduct of the clinical trial.

The Code of Conduct, a collection of goals and considerations that govern the ethical and scientific conduct of clinical investigations sponsored by Merck, is provided in Section 12.1 - Merck Code of Conduct for Clinical Trials.

The investigator also agrees to allow monitoring, audits, IRB/ERC review and regulatory authority inspection of trial-related documents and procedures and provide for direct access to all trial-related source data and documents.

The investigator agrees not to seek reimbursement from subjects, their insurance providers or from government programs for procedures included as part of the trial reimbursed to the investigator by the Sponsor.

The investigator shall prepare and maintain complete and accurate trial documentation in compliance with Good Clinical Practice standards and applicable federal, state and local laws, rules and regulations; and, for each subject participating in the trial, provide all data, and, upon completion or termination of the clinical trial, submit any other reports to the Sponsor as required by this protocol or as otherwise required pursuant to any agreement with the Sponsor.

Trial documentation will be promptly and fully disclosed to the Sponsor by the investigator upon request and also shall be made available at the trial site upon request for inspection, copying, review and audit at reasonable times by representatives of the Sponsor or any regulatory authorities. The investigator agrees to promptly take any reasonable steps that are requested by the Sponsor as a result of an audit to cure deficiencies in the trial documentation and worksheets/case report forms.

The investigator must maintain copies of all documentation and records relating to the conduct of the trial in compliance with all applicable legal and regulatory requirements. This documentation includes, but is not limited to, the protocol, worksheets/case report forms, advertising for subject participation, adverse event reports, subject source data, correspondence with regulatory authorities and IRBs/ERCs, consent forms, investigator's curricula vitae, monitor visit logs, laboratory reference ranges, laboratory certification or quality control procedures and laboratory director curriculum vitae. By signing this protocol, the investigator agrees that documentation shall be retained until at least 2 years after the last approval of a marketing application in an ICH region or until there are no pending or contemplated marketing applications in an ICH region or until at least 2 years have elapsed since the formal discontinuation of clinical development of the investigational product. Because the clinical development and marketing application process is variable, it is anticipated that the retention period can be up to 15 years or longer after protocol database lock. The Sponsor will determine the minimum retention period and notify the investigator when documents may be destroyed. The Sponsor will determine the minimum retention

period and upon request, will provide guidance to the investigator when documents no longer need to be retained. The sponsor also recognizes that documents may need to be retained for a longer period if required by local regulatory requirements. All trial documents shall be made available if required by relevant regulatory authorities. The investigator must consult with and obtain written approval by the Sponsor prior to destroying trial and/or subject files.

ICH Good Clinical Practice guidelines recommend that the investigator inform the subject's primary physician about the subject's participation in the trial if the subject has a primary physician and if the subject agrees to the primary physician being informed.

The investigator will promptly inform the Sponsor of any regulatory authority inspection conducted for this trial.

Persons debarred from conducting or working on clinical trials by any court or regulatory authority will not be allowed to conduct or work on this Sponsor's trials. The investigator will immediately disclose in writing to the Sponsor if any person who is involved in conducting the trial is debarred or if any proceeding for debarment is pending or, to the best of the investigator's knowledge, threatened.

In the event the Sponsor prematurely terminates a particular trial site, the Sponsor will promptly notify that trial site's IRB/IEC.

According to European legislation, a Sponsor must designate an overall coordinating investigator for a multi-center trial (including multinational). When more than one trial site is open in an EU country, Merck, as the Sponsor, will designate, per country, a national principal coordinator (Protocol CI), responsible for coordinating the work of the principal investigators at the different trial sites in that Member State, according to national regulations. For a single-center trial, the Protocol CI is the principal investigator. In addition, the Sponsor must designate a principal or coordinating investigator to review the trial report that summarizes the trial results and confirm that, to the best of his/her knowledge, the report accurately describes the conduct and results of the trial [Clinical Study Report (CSR) CI]. The Sponsor may consider one or more factors in the selection of the individual to serve as the Protocol CI and or CSR CI (e.g., availability of the CI during the anticipated review process, thorough understanding of clinical trial methods, appropriate enrollment of subject cohort, timely achievement of trial milestones). The Protocol CI must be a participating trial investigator.

